The severe acute respiratory syndrome coronavirus 2 (SARS-CoV-2) has rapidly instigated a global pandemic. As of this writing, there are approximately 65 million documented cases of infection worldwide, and over 1.5 million deaths. In the United States (US), coronavirus disease 2019 (COVID-19) has disrupted the economy, overwhelmed healthcare system, led to widespread school cancellations, and caused more than 274,000 deaths since March 2020. A vaccine against COVID-19 is widely viewed as the key to controlling the pandemic and enabling a return to “normal” life. Vaccine development is proceeding at an unprecedented pace with 10 vaccines currently in phase 3 trials. Experts have projected that a safe and effective vaccine may be available by mid-2021. At the same time, a growing body of evidence indicates that a significant proportion of adults in the U.S. may not accept vaccination against COVID-19. Even more alarming, COVID-19 vaccine hesitancy (refusal or reluctance to accept a vaccine) appears to be increasing as the vaccine approval process becomes increasingly politicized. Just as efforts to develop vaccine production and delivery capacity have been undertaken in advance of having a proven effective vaccine, parallel efforts are needed to identify effective messages and communication strategies to overcome COVID-19 vaccine hesitancy.

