Our team recently surveyed a nationally representative sample of approximately 1,000 adults in the United States and found that only 57% intended to be vaccinated when a coronavirus vaccine becomes available.¹ This percentage was even lower among people who identified as Black or Hispanic (39% and 43% respectively), those with a high school education or less (46%) and those in the lowest income groups (49% of those reporting a household income of \$30,000 or less, compared to 72% of those reporting a household income of \$100,000 or more). We asked those who indicated they would not or might not get vaccinated for their reasons and found that some individuals may be willing to be vaccinated if provided specific information about the vaccine such as side effects and effectiveness. Others expressed generalized skepticism, fear and distrust of vaccines, with some even referring to anti-vaccine conspiracy theories. Our findings are consistent with an extensive body of research documenting that people often do not behave rationally and highlight the urgent need to proactively develop and test interventions to maximize vaccination rates when a coronavirus vaccine becomes available.²⁻⁶ To address this need, our goals in the present study are to create and test targeted messages to address the concerns of subgroups of people at risk for not being vaccinated, with the ultimate goal of maximizing vaccine uptake when a vaccine for COVID-19 becomes available. We will accomplish this by working with an existing online panel of volunteers, which will allow efficient, focused data gathering. Results of the first round of the survey will provide a nuanced, current description of how vulnerable adults perceive the coronavirus and forthcoming vaccines, which will be used as the basis for developing messages and communication strategies. In the second round, we will test different versions of messages intended to reduce vaccine hesitancy and support uptake. This project will ultimately result in a set of tested, evidence-derived messages about vaccination for COVID-19. We will make these messages available, together with evidence how these influence members of vulnerable populations' understanding of vaccination, and disease risk, as well as intent to be vaccinated. The messages will be freely available for use by organizations and providers seeking to improve communication about a coronavirus vaccine.

6. Inclusion and Exclusion Criteria*

Inclusion Criteria.

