Participants will be recruited from an existing online research panel (Prolific). Prolific verifies participants at the time they register with Prolific and assigns participants a Prolific study ID. Prolific will post the invitation to our survey to the dashboard of eligible participants registered on their site. The survey title, duration, and payment amount will be displayed in the dashboard of eligible participants, as well as a link to the online survey. Surveys will be programmed in Research Electronic Data Capture (REDCap) - an online survey application. Participants' survey responses will be collected anonymously.

If a participant elects to respond to the survey, they will be taken to a REDCap survey. The survey will include questions that assess participants' intent to be vaccinated when a COVID-19 vaccine is available, as well as participants' knowledge, beliefs, and attitudes about COVID-19, vaccines in general, and a COVID-19 vaccine.

In one section of the survey, we will ask participants to imagine they are at a routine follow up visit with their primary care provider. Participants will be randomized to several brief, hypothetical messages from their provider regarding vaccination after which participants' intent to be vaccinated will be re-assessed. See table 1 for questionnaire domains and sample items.

Table 1. Sample Survey Domains and Items

Sample Domains	Sample Items
Personal risk I – disease overall	What is your best guess as to whether you will get the coronavirus within the next 6 months ?
Vaccination intent	When a vaccine for the coronavirus becomes available, will you get vaccinated?
Message testing	Imagine that you are seeing your doctor for an annual physical exam. Near the end of the appointment, your doctor says, “We have the COVID-19 vaccine available today. I’ve taken a careful look at the studies and the results are very impressive. They show that it’s very safe and very effective. This is the best way to protect yourself from this virus. I recommend you get it.”
Risk Beliefs	The COVID-19 pandemic is a hoax.
Knowledge of COVID-19	If 100 people your age were infected with COVID-19, about how many would need to be hospitalized?

Attitudes towards vaccine - general	Vaccines are one of the most important medical advances ever developed.
Attitudes towards COVID-19 vaccine specifically	The COVID-19 vaccine has been developed too quickly.
Vaccine knowledge	Vaccines don't work against viruses.

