Vaccination norms and values	Most of the people I know will get vaccinated against COVID-19.
Personal experience with COVID-19	Have any of your friends and family members have become very ill or died of COVID-19?
Vaccination behavior (past and future)	Thinking back over the past 5 years, how many of those years did you get a flu shot?
Demographics and other characteristics	Age, gender, education, etc.

Participants will receive a small payment as recommended by the panel vendor, valued at approximately \$3.00 to \$3.50 for a 20-minute survey. The final amount will depend on the final estimated survey completion time and an hourly rate selected to maximize participation and the number of participants. The hourly rate range required by the survey vendor is \$6.50/hr- \$12.50/hr). Payment will be made directly by the online research panel to participants after survey completion.

12. Data and Specimen Banking*

No specimens are being collected as part of the research. We will maintain a limited dataset for analysis at the completion of the study.

13. Data Analysis and Management*

Data will be stored on University of Massachusetts Medical School computers and/or Meyers Primary Care Institute computers. We will not collect any information that will allow us to identify participants. All contact with participants will be via the online vendor, which has assigned a unique study id to each participant.

We will examine response distributions of each variable and associations between variables (e.g., correlations between perceived personal risk and tendency to engage in protective behavior).

We will test the impact of different communication strategies that providers might use to recommend COVID-19 vaccination using t-tests, chi-squares, and regression models to compare vaccination intent according to which message participants received. Appropriate statistical tests will be chosen depending on specific variables and their distributions.

14. Provisions to Monitor the Data to Ensure the Safety of Subjects*

The proposed study involves no more than minimal risk to participants.

To ensure that participants have access to current, accurate information about the coronavirus, we will provide the web address to the main Centers for Disease Control (CDC) website (<https://www.cdc.gov/>), which contains information and resources related to the coronavirus pandemic.

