We will await review and approval by the Institutional Review Board of the University of Massachusetts Medical School prior to the initiation of any study activities.

We will not receive or request information that would allow us to identify participants. We will have only their responses to the survey questions, and their Prolific study ID (which consists of a string of approximately 20 numbers and letters). We will never have access to a key which would allow us to link the Prolific id to participants' name, email, address or phone number. All data will be collected electronically via the Prolific online platform and REDCap. All computerized data will be kept on secured computers or networks. These data will be accessible only to research staff, using confidential usernames and passwords. Published data will not contain any individual identifiers.

15. Withdrawal of Subjects Without Their Consent*

Because our data collection from participants will occur via survey, we do not anticipate the need to actively withdraw participants. Participants whose response is very incomplete or shows significant signs of inattention to the survey, highly contradictory responses, or nonsensical text in response to open ended items will be omitted from analyses.

16. Risks to Subjects*

Potential Risks to Subjects

The proposed study poses minimal risks to the study subjects. The risks that do exist fall within three categories: a) risks associated with participating in research surveys; and b) risks associated with the research content area. Our procedures for protecting against such risks are described below.

Risks Associated with Participating in Research Surveys. Subjects will be recruited to participate in online surveys. It is possible some participants will perceive these as be time-consuming or frustrating to complete. Our procedures for protecting against such risks are described below.

Risks Associated with the Research Content Area. We recognize that the content of the survey (i.e., reaction to the coronavirus and its dangers) may be emotionally sensitive. Our procedures for protecting against such risks are described below.

Adequacy of Protection Against Risks

Informed Consent

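### Section 13 does not plan to adjust the message comparison for pre-message intent, or to estimate the effect in people not already intending to be vaccinated

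*Combined protocol and SAP*

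**What the plan says.** - **Design (Section 11).** Participants are randomised to brief hypothetical messages from their provider, after which their "intent to be vaccinated will be re-assessed". Table 1 lists a separate vaccination-intent item, "When a vaccine for the coronavirus becomes available, will you get vaccinated". The order of the items is not printed. That the intent item comes before the message is an inference from the word re-assessed.
- **Analysis (Section 13).** The plan for the message comparison is "t-tests, chi-squares, and regression models to compare vaccination intent according to which message participants received", followed by "Appropriate statistical tests will be chosen depending on specific variables and their distributions". No baseline covariate, change score, interaction or subgroup is named here or in any other section.
- **Endpoint (Section 10).** The primary endpoint is intent to be vaccinated. The section does not say whether this is the pre-message answer, the post-message answer or the change.
- **Aim (Sections 4 and 5).** Objective 2 is to develop and test messages for vaccine-hesitant subgroups. The Background defines hesitancy as refusal or reluctance, and says "In the second round, we will test different versions of messages intended to reduce vaccine hesitancy and support uptake".
- **Who is enrolled (Sections 6 and 25).** Adult panel members who can complete the survey in English, with no exclusions and no screen on intent; 1000 to 3500 people are expected.
- **Prior intent (Section 5).** In the team's earlier national survey 57% intended to be vaccinated.

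**The concern.** Two things are left unused. First, a person's intent before the message is likely to be a strong predictor of intent after it. Leaving it out of the comparison gives up precision that an answer already collected could restore. Second, if many participants already say *yes*, a whole-sample comparison dilutes any effect among those who do not, and they are the people Objective 2 is about.

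Because Section 13 leaves the choice of test open, both the adjustment and the subgroup could also be chosen after the results by message have been seen. At stake are the precision of the message comparison and a prespecified answer to the question the objective asks.

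**Working it through.** The plan gives no alpha, power, effect size, number of arms or sample-size calculation, so there is no stated figure to reproduce. The wording of Section 13 settles the omission. The arithmetic below only shows what it could cost.

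**Inputs from the protocol.** Prior *yes* 57% (Section 5, a different sample); N = 1000 or 3500 (Section 25).

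**Assumed.** A yes/no item; one message per person; four equal arms, so n = 250 or 875 per arm; all N randomised; conversion to *yes* among the other 43% of 10% versus 20%; no message effect among prior *yes* respondents; a share r of prior *yes* answers staying *yes* in both arms; one uncorrected pairwise test at two-sided 0.05. The message item speaks of a vaccine that is "We have the COVID-19 vaccine available today", whereas the intent item is about a future vaccine, so r may be well below 1. I use 60% to 90%.

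**Dilution.** Whole-sample effect d = 0.43 × (0.20 − 0.10) = 0.043, that is, 4.3 points.

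**Variances.** With mean conversion c = 0.15:
- overall proportion P = 0.57r + 0.43c
- unadjusted variance = P(1 − P)
- variance within pre-message strata = 0.57r(1 − r) + 0.43c(1 − c)

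At r = 0.9, P = 0.5775. The unadjusted variance is 0.2440 and the within-stratum variance is 0.0513 + 0.0548 = 0.1061, a ratio of 2.3. The ratio is 1.7 at r = 0.8 and 1.3 at r = 0.6. Adjustment is worth that multiple of participants.

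**Power.** z = d / √(2V/n), and power ≈ Φ(z − 1.96) plus a negligible opposite tail. At r = 0.9:
- n = 250: adjusted z = 0.043/0.0291 = 1.48, power 31%; unadjusted z = 0.043/0.0442 = 0.97, power 16%.
- n = 875: adjusted z = 0.043/0.0156 = 2.76, power 79%; unadjusted z = 0.043/0.0236 = 1.82, power 44%.

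**Not-*yes* group alone.** It has 0.43n = 107.5 or 376 per arm and variance 0.15 × 0.85 = 0.1275. Then z = 0.10/0.0487 = 2.05 (54%) and 0.10/0.0260 = 3.84 (97%). Retention does not enter.

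Simulation (40,000 comparisons per setting; the adjusted test is the score test for message in a logistic model with pre-message *yes* / not *yes*) agrees, with type I error of 5.0-5.1%:

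| Conversion | N | Unadjusted | Adjusted, r = 60% / 80% / 90% | Not-*yes* group alone |
|---|---|---|---|---|
| 10% vs 20% | 1000 | about 17% | 19 / 24 / 32% | about 54% |
| 10% vs 20% | 3500 | about 45% | 54 / 65 / 79% | about 97% |
| 10% vs 15% | 1000 | about 8% | 9 / 10 / 12% | about 20% |
| 10% vs 15% | 3500 | about 15% | 18 / 23 / 30% | about 55% |

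**If the no-effect assumption fails.** Suppose the message also lowers retention from 95% to 90%. The whole-sample effect shrinks to 0.043 − 0.57 × 0.05 = 0.0145. Unadjusted and adjusted power are then about 6% and 8% at N=1000, and 9% and 17% at N=3500.

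**Why the subgroup needs its own model.** In a logistic model with a message-by-prior-intent term and not-*yes* as reference, the message coefficient is the effect in the not-*yes* group: ln[(0.20/0.80)/(0.10/0.90)] = ln 2.25 = 0.81. Without the interaction it is about 0.41 (simulated at r = 0.9, N = 3500). One coefficient cannot serve as both the main adjusted effect and the subgroup effect. The interaction may also be inestimable when nearly all prior *yes* answers stay *yes*, or when the skipped category is small.

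**The case against.** **The plan may already intend this.** Section 13 lists regression alongside t-tests and chi-squares, and regression on message alone would add little to those tests, so covariates are a natural reading. Asking about intent a second time also suggests that the first answer is meant to be used. This stands as far as it goes: the text permits adjustment, and a reader should not infer that the team will ignore the earlier answer. But permitting is not planning, and the choice is expressly left open.

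**It is a pilot.** How much model detail a pilot should fix in advance is partly a matter of judgement. That supports treating this as an improvement. It does not argue against it, since the study is meant to yield tested messages for others to use and the change costs only wording.

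**The subgroup is one choice among several.** Objective 2 speaks of subgroups in the plural, and the Background also describes low intent by race or ethnicity, education, income and reasons for hesitancy. One pooled not-*yes* group merges people who might not be vaccinated with those who would not. This stands. The pooled group follows the Background's own definition of hesitancy but does not exhaust the objective, so its estimate should be secondary.

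**The figures are driven by assumptions.** Message testing belongs to the second round, whose mix of participants is not described. The 57% comes from another sample, and the t-tests suggest that a scored scale may be used. All of this stands. The power figures would not transfer to a scored item.

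**A reader might infer that Section 15 would remove people whose mind the message changed**, because "highly contradictory responses, or nonsensical text in response to open ended items will be omitted from analyses". Nothing there says that a change of intent counts as a contradiction, so the documents do not support that step and no change to Section 15 is asked for here.

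**Conclusion.** The point holds as a free improvement. Section 13 does not plan to use the pre-message answer that Section 11 implies, and plans no estimate among people not already intending to be vaccinated.

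Two stronger readings are not supported. One is that the planned comparison is biased or invalid; randomisation makes the unadjusted comparison unbiased. The other is that the study is shown to be underpowered; the protocol states no arms, effect size or power target against which to judge that.

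Under the illustrative assumptions with 60% to 90% retention, adjustment raises power from about 17% to 19-32% (N=1000) and from about 45% to 54-79% (N=3500). In the not-*yes* group power is about 54% and 97%. With 10% versus 15% conversion, adjusted power is only about 9-12% and 18-30%, against about 8% and 15% unadjusted. Both gains come largely from setting aside the same variation between prior *yes* and not-*yes* respondents. They overlap and must not be added. Confidence is medium, because the item order is inferred and the sizes depend on assumed conversion, arms, retention and response scale.

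**What to change.** In Section 13:

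1. **Main message analysis.** State that it is a regression of post-message intent on message, adjusted for pre-message intent. Keep skipped pre-message answers as their own category. Set the model form by the response scale of the item, not by the observed data: logistic for yes/no, ordinal for ordered categories, linear for a numeric score.
2. **Secondary analysis.** Estimate the message effect among participants who did not answer *yes* before the message, by fitting the model in that subgroup alone. Fix in advance which responses count as not-*yes*, including how a skipped answer is treated. Do not take this estimate from an interaction in the main model.

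The cost is wording only. If the pre-message item is in the survey as Section 11 implies, no extra items, participants or money are needed. The text should be settled before responses are examined by message.
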